## 6.1.12. Columbia Suicide Severity Rating Scale (C-SSRS)

The C-SSRS is a questionnaire designed for the assessment of suicidal ideation and behaviour in adolescents and adults.

The C-SSRS will assess suicidality over the month preceding Screening as well as over the subject's lifetime. At Screening, the "Baseline/Screening" version of the scale will be used, and at subsequent visits the "Since Last Visit" version of the scale will be used. Versions of the instrument relevant to the subject's native language (ie, English) should be used. C-SSRS evaluations will be undertaken at the timepoints indicated in Table 6-1.

The questionnaire must be administered by an Investigator or other individual that is suitably qualified by education or training. See APPENDIX 7 for a sample C-SSRS –Baseline/Screening version assessment and APPENDIX 8 for a sample C-SSRS-Since Last Visit version assessment.

If there is a positive result for suicidality on the C-SSRS after Screening (defined by a subject answering "yes' to questions 4 or 5 on the suicidal ideation portion of the C-SSRS), the subject will be evaluated by an Investigator or medically qualified Sub-investigator for continuation in the study.

If a subject becomes suicidal during the study, an Investigator should provide the appropriate treatment to the subject.

# 6.1.13. Clinical Opioid Withdrawal Scale (COWS)

The naloxone HCl challenge will be conducted as indicated in Table 6-1 for eligible subjects. Clinical Opioid Withdrawal Scale is a clinician-administered, pen and paper instrument that rates 11 common opiate withdrawal signs or symptoms. The summed score of the eleven items can be used to assess a subject's level of opiate withdrawal and to make inferences about their level of physical dependence on opioids (Wesson and Ling, 2003). The scale must be administered by an Investigator or other individual that is suitably qualified by education or training. See APPENDIX 9 for a sample of COWS.

# 6.1.14. Assessment of Respiratory Depression

Capnography alarms will be set to evaluate for respiratory depression and will include:

- An increase in EtCO2 of at least 10 mmHg compared to baseline or >50 mmHg, whichever value is the lowest
- A reduction in O2 saturation to <92%
- A reduction in respiratory rate to <6 breaths per minute

All alarms will be assessed for clinical significance and reported as AEs, as applicable. Supplemental oxygen will be given as medically necessary. Events will be timed using a stopwatch or equivalent to confirm clinical relevance. Interventions used to treat respiratory depression will be documented.

## 6.1.15. Medical Interventions for Signs of Respiratory Depression

In the event that subjects show signs and symptoms of respiratory depression, the Investigator or study staff will begin intervention procedures that may escalate in the degree of intervention as follows:

- Verbal stimuli: Call the subject's name loudly. If no response and/or no improvement in respiratory depression, proceed to physical stimuli.
- Physical stimuli: Apply sternal rub to subject and/or apply nail bed pressure. If subject is unable to be aroused and/or there is no improvement in signs of respiratory depression, proceed to O2 administration and prepare for possible naloxone administration (if there is no improvement with verbal or physical stimuli, there is a high likelihood of requiring naloxone administration).
- O2 administration: Administer oxygen with a target SpO2 of 95-100%. Prepare naloxone for administration if no improvement in respiratory depression clinical parameters or as per Investigator discretion.
- Naloxone administration: Administer naloxone (eg, 4 mg/spray IN every 2-3 minutes; 0.4 mg IV every 2-3 minutes to a maximum of 10 mg) and titrate until adequate oxygenation/ventilation is achieved.

The Investigator or designee will choose the appropriate level of intervention as deemed medically necessary. Subjects who receive intervention will be evaluated to determine if further intervention (eg, hospitalization) is warranted. Subjects who show significant signs of respiratory depression that requires naloxone administration or poses significant safety concerns may be withdrawn from the study at the discretion of the Investigator or designee.

# 6.1.16. Rescue Therapy

The clinical study site is equipped with emergency equipment and supplies that correspond with the level of risk associated with this study. In case of a medical emergency or an SAE requiring medical intervention, emergency equipment and supplies will be available and will include, but may not be limited to, stocked crash carts, oxygen source, suction pump, and defibrillator. Emergency medication (eg, naloxone) or rescue medication required for advanced cardiac life support may be administered if deemed necessary by an Investigator or designee. If required, subjects will be transported to a hospital.

During the Qualification and Treatment periods, the PI or designee will be on-site at the time of study drug administration until at least 6 hours postdose. Advanced cardiac life support-certified staff will be present on site and an Investigator will be readily available by telephone. When not available on-site, the PI or designee will be on-call until the end of the study. While confined in the CRU, subjects will be supervised by staff nurses and/or paramedics. Dedicated nurses and/or paramedics will be available to monitor AEs and perform safety measures. The date and time of rescue medication administration as well as the name and dosage regimen of the rescue medication will be recorded.

# 6.2. Pharmacokinetic Assessments

# 6.2.1. Pharmacokinetic Blood Sampling

The complete blood sampling schedule for morphine and its metabolites is presented in Table 6-14. The complete blood sampling schedule for AZD4041 is presented in Table 6-15.

# Table 6-14Pharmacokinetic Blood Sampling Schedule for Morphine and its
Metabolites

#### Pharmacokinetic Blood Sampling - Scheduled Timepointsa

Day 1: predose, 5, 15, 30 minutes and 1, 1.5, 2, 3, 4, 6, 8, 12, 24, and 36 hours postdose

Day 15: predose, 5, 15, 30 minutes and 1, 1.5, 2, 3, 4, 6, 8, 12, 24, 36, 48, and 72 hours postdose

a Predose is relative to the start of morphine intravenous infusion. Nominal times listed are relative to the end of morphine intravenous infusion.

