	Neurological examination findings
	C-SSRS findings
	• Type of medical intervention used, summarized for each event of significantly increased EtCO 2 , reduced SpO 2 , or respiratory rate
To assess the PK of AZD4041 and morphine in healthy recreational opioid users	Plasma concentrations as well as PK parameters for AZD4041 and morphine and its metabolites as described in Section 8.4
To assess the impact of multiple dose administrations of AZD4041 on the PK of morphine and its metabolites	Plasma concentrations as well as PK parameters for AZD4041 and morphine and its metabolites as described in Section 8.4
To assess the impact of morphine on steady-state PK of AZD4041	Plasma concentrations as well as PK parameters for AZD4041 and morphine and its metabolites as described in Section 8.4
To assess the renal clearance of AZD4041	Urine concentrations as well as PK parameters for AZD4041 as described in Section 8.4

Abbreviations: AE = adverse event; C-SSRS = Columbia-Suicide Severity Rating Scale; ECG = electrocardiogram EtCO2 = end tidal carbon dioxide; PK = pharmacokinetic; SpO2 = oxygen saturation.

[figure not shown]

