## 5.3. Administration of Study Drug

Study treatments as described in Section 3.2 will be administered in the morning. The date and time of each dose will be recorded. For each subject, Day 1 to Day 14 scheduled postdose activities and assessments will be performed relative to the time of AZD4041/placebo administration or end of morphine infusion. From Day 15, all scheduled postdose activities will be performed relative to the end of morphine infusion, with the exception of PK sampling for AZD4041.

On Day 1, a single intravenous infusion of morphine will be administered to the subjects over a 10-minute interval ( $\pm$  30 seconds) in the morning.

On Days 2 to 15, an oral dose of the assigned treatment (either AZD4041 or Placebo) once daily will be administered to subjects using a syringe for 14 consecutive days. The dose will be administered directly into the subject's mouth.

On the morning of Day 15, the oral dose of the assigned treatment (either AZD4041 or Placebo) will be combined with a single intravenous infusion of morphine. A single intravenous infusion of morphine will be administered to the subjects over a 10-minute interval ( $\pm$  30 seconds). The assigned treatment (AZD4041 or Placebo) will then be administered orally immediately (within 1 minute) after the end of morphine infusion.

The study drugs will be dispensed only to eligible subjects and administered under the supervision of study personnel. Treatment compliance will be verified according to the site's standard operating procedures (SOPs).

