# Table 6-15Pharmacokinetic Blood Sampling Schedule for AZD4041Pharmacokinetic Blood Sampling - Scheduled Timepointsa

Days 2 to 7: predose

Day 8: predose, 5, 15, 30 minutes and 1, 1.5, 2, 3, 4, 6, 8, and 12 hours postdose

Days 9 to 14: predose

Day 15: predose, 5, 15, 30 minutes and 1, 1.5, 2, 3, 4, 6, 8, 12, 24, 36, 48, and 72 hours postdose

a. Nominal times listed are relative to the time of AZD4041 administration.

Blood samples will be collected by direct venipuncture into a labeled tube containing the appropriate anticoagulant as specified by the bioanalytical facility. As an option to the subject or if judged necessary by the clinical staff, blood samples may be collected from an indwelling cannula which will be placed in the vein of the subject.

The actual time of all PK blood draws will be recorded and reported for all subjects.

Windows for timed PK blood sample collections are presented in Table 6-16. PK samples collected outside of the pre-specified windows will be documented as protocol deviations. Since actual times are to be used for the PK analysis, deviations will be reflected in the analysis unless indicated otherwise upon review of the data.

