# Table 6-16Acceptable Windows for Timed PK Blood Specimen Collection
Procedures

Elapsed Time	Accepted Window
Predose	within 5 minutes a
$> 0$ hour to $\le 30$ minutes	$\pm 1$ minute
$> 30$ minutes to $\le 4$ hours	$\pm 2$ minutes
> 4 hours to $\leq 12$ hours	$\pm$ 5 minutes
> 12 hours to $\leq$ 24 hours	$\pm 10$ minutes
> 24 hours to 72 hours	$\pm 2$ hours

a. On Day 1 and Day 2, the accepted window can be increased to within 60 minutes.

AZD4041, morphine, morphine-6-glucuronide, and morphine-3-glucuronide concentrations for PK assessments will be obtained through bioanalysis of the plasma derived from the blood samples drawn during this study, using validated bioanalytical methods.

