# 8.4.1. Pharmacokinetic Parameters

The PK parameters will be determined by non-compartmental analysis using appropriate software. The PK parameters for AZD4041, morphine, morphine-6-glucuronide and morphine-3-glucuronide are presented in Table 8-1.

Parameter a	Definition		
For morphin	For morphine, morphine-6-glucuronide and morphine-3-glucuronide (Day 1 and 15)		
C max	Maximum observed concentration occurring at time t max		
t max	Time of maximum observed concentration. If the maximum observed concentration is not unique, then the first maximum is used		
AUC 0-t	Area under the concentration time curve from the time of last dosing to the time of last quantifiable concentration $(T_{last})$		
AUC 0-∞	Area under the concentration time curve extrapolated to infinity, calculated as $AUC_{0-T} + C_{last}/\lambda_Z$ , where $C_{last}$ is the last quantifiable concentration at time $T_{last}$		
t 1/2,z	Terminal elimination half-life, calculated as $ln(2)/\lambda$		

 Table 8-1 Pharmacokinetic Parameters in Plasma

Parameter a	Definition		
T last	Time of last measurable observed concentration		
CL	Total body clearance, calculated as $Dose/AUC_{0-\infty}$ (parent drug only)		
Vz	Volume of distribution based on terminal phase (parent drug only)		
	For AZD4041		
Days 2 to 7 and Days 9 to 14:			
Ctrough	Predose concentration observed immediately prior to the next successive dose		
Days 8 and 15			
C max,ss	maximum observed plasma concentration		
t max,ss	time to maximum observed plasma concentration		
C trough	Predose concentration observed immediately prior to the next successive dose		
AUC τ	area under the concentration time curve over the dosing interval at steady- state, calculated from 0 to 24 hours (dosing interval)		
C av	average concentration during a dosing interval, after the last dose of a multiple dose regimen, calculated as AUC $\tau/\tau$		
t 1/2,z	Terminal elimination half-life, calculated as $ln(2)/\lambda_z$ (Day 15 only)		
CLss/F	Apparent total body clearance at steady-state, calculated as $Dose/AUC_{\tau}$		
Vzss/F	Apparent volume of distribution at steady-state, based on terminal phase		

a. A complete list of PK parameters that will be used for PK calculation and presented in the PK listings will be included in the SAP.

Parameter	Definition

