## 8.4.3.2. Comparison of PK Parameters

Two-sided 90% confidence interval of the ratio of geometric LSmeans obtained from the ln-transformed PK parameters ( $C_{max}$ , AUC0-t, and AUC0- $\infty$  for morphine and its metabolites;  $C_{max,ss}$  and AUC $\tau$  for AZD4041) will be calculated to assess the magnitude of interaction for the following comparisons:

- Morphine and its metabolites: Morphine + AZD4041 (Day 15) versus Morphine alone (Day 1)
- 2. AZD4041: Morphine + AZD4041 (Day 15) *versus* AZD4041 (Day 8)

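### Morphine and its metabolites are sampled to 36 h on Day 1 but to 72 h on Day 15, so the Day 15/Day 1 AUC0-t ratio can exceed 1 with no interaction, and no matched-interval ratio is planned beside it

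*Protocol*

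**What the plan says.** Protocol Table 6-14 sets the blood sampling for morphine, morphine-6-glucuronide (M6G) and morphine-3-glucuronide (M3G), in time from the end of infusion. For the morphine-alone dose the row reads "Day 1: predose, 5, 15, 30 minutes and 1, 1.5, 2, 3, 4, 6, 8, 12, 24, and 36 hours postdose". The row for the second morphine dose, given with AZD4041 or placebo, keeps all of these times and adds two later ones, at 48 h and 72 h.

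Protocol Table 8-1 defines AUC0-t as "Area under the concentration time curve from the time of last dosing to the time of last quantifiable concentration", and SAP Table 8-2 defines it in the same way. Neither gives a fixed end time.

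Protocol 8.4.3.2 says that 90% confidence intervals for ratios of Cmax, AUC0-t and AUC0-inf "will be calculated to assess the magnitude of interaction for the following comparisons"; for morphine and its metabolites the comparison is Day 15 with AZD4041 against Day 1 alone. SAP 8.5.2 repeats these ratios for Sequence 1 and adds the Day 1 and Day 15 comparison for Sequence 2 (placebo). They serve a secondary objective: "To assess the impact of multiple dose administrations of AZD4041 on the PK of morphine and its metabolites".

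The AUC is computed on actual times: "Since actual times are to be used for the PK analysis, deviations will be reflected in the analysis". The Table 6-16 row "> 24 hours to 72 hours" allows ±2 hours.

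Neither document defines AUC0-36h, cuts Day 15 at 36 h, or says how the unequal intervals are to be read.

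**The concern.** The numerator of the AUC0-t ratio can cover 72 h, while the denominator stops at a nominal 36 h (34 to 38 h within the window). Any area counted after 36 h on Day 15 has no counterpart on Day 1. An AUC0-t ratio above 1 could therefore reflect the sampling schedule and not AZD4041, and a real fall in exposure could be hidden. The question being asked is whether AZD4041 changes opioid exposure, so a false signal in either direction would be unwelcome even for a secondary objective.

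**Working it through.** **What is and is not given.** The documents state no figure on this point, so there is none to reproduce. From Table 6-14: last nominal sample 36 h (Day 1) and 72 h (Day 15, with one at 48 h). The documents give no half-life, LLOQ or share of AUC in the terminal phase. Half-lives h = 5, 8, 10, 15 and 20 h are assumptions, chosen to show a range.

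**Direction.** Day 15 AUC0-t = AUC0-36h + AUC from 36 h to tlast. With identical profiles on both days, the second term is positive whenever a 48 h or 72 h value counts, so the ratio exceeds 1. If both late samples are non-quantifiable (NQ), the second term is zero and the schedule causes no bias.

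**Size with no interaction.** Let f be the share of AUC in the terminal phase and T the last quantifiable time on Day 15:

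ratio = (1 − f·2^(−T/h)) / (1 − f·2^(−36/h)); Day 1 AUCextr = f·2^(−36/h).

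Example, h = 10 h, f = 1, T = 72 h: (1 − 0.0068)/(1 − 0.0825) = 1.082, with Day 1 AUCextr 8.2%.

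| h (h) | f = 1, T = 72 h | f = 1, T = 48 h | Day 1 AUCextr (f = 1) | f = 0.3, T = 72 h | f = 0.3, T = 48 h |
|---|---|---|---|---|---|
| 5 | 1.007 | 1.006 | 0.7% | 1.002 | 1.002 |
| 8 | 1.044 | 1.030 | 4.4% | 1.013 | 1.009 |
| 10 | 1.082 | 1.051 | 8.2% | 1.023 | 1.014 |
| 15 | 1.189 | 1.099 | 18.9% | 1.049 | 1.026 |
| 20 | 1.287 | 1.137 | 28.7% | 1.067 | 1.032 |

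For scale, with 24 paired completers and an assumed within-subject CV of 20%, the 90% CI half-width is a factor exp(1.714 × √ln(1.04) × √(2/24)) = 1.10. The largest ratios in the table would exceed it.

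**With a true interaction.** Multiply clearance by k, with the same volume and f = 1. The true ratio is 1/k.

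- Existing AUC0-t ratio = (1/k)(1 − 2^(−kT/h)) / (1 − 2^(−36/h))
- Matched AUC0-36h ratio = (1/k)(1 − 2^(−36k/h)) / (1 − 2^(−36/h))

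For clearance down 30% (k = 0.7, true 1.429):

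| h (h) | AUC0-t, T = 72 h | AUC0-t, T = 48 h | Matched AUC0-36h |
|---|---|---|---|
| 5 | 1.437 | 1.425 | 1.395 |
| 8 | 1.476 | 1.413 | 1.326 |
| 10 | 1.510 | 1.405 | 1.286 |
| 15 | 1.591 | 1.389 | 1.212 |
| 20 | 1.655 | 1.379 | 1.167 |

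For clearance up 25% (k = 1.25, true 0.80), matched gives 0.804 to 0.886, and AUC0-t to 72 h gives 0.805 to 1.073.

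Counting which ratio lies nearer 1/k over the ten combinations of h and T, matched is nearer in:

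| Clearance change | Matched nearer |
|---|---|
| none | 10 of 10 |
| down 5% | 10 of 10 |
| down 10% | 9 of 10 |
| down 20% | 3 of 10 |
| down 30% | 0 of 10 |
| up 25% | 10 of 10 |

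Neither ratio dominates.

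**Why a matched interval needs an exact end time.** If the 36 h sample fell at 34 h on Day 1 and 38 h on Day 15 in every subject, the no-interaction ratio would be (1 − 2^(−38/h))/(1 − 2^(−34/h)) = 1.004, 1.016, 1.025, 1.044 and 1.058 for the five half-lives, and the inverse if reversed. This is the extreme of the window, and it is a property of the added parameter, not of the current plan.

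**The case against.** The strongest reply is that the size is unproven and that the plan already holds the means to detect the problem.

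- Ratios above 1.1 need one-phase decline, a half-life of 15 h or more, and for 15 h a quantifiable 72 h sample. This is right, and the bias may be nil.
- SAP 8.1 normally ends a profile after two or more consecutive NQ values. This limits the problem but does not equalise the two days.
- AUC0-inf is planned with its own 90% CI and targets the same quantity on both days. This stands. However, its terminal slope can use points to 72 h on Day 15 and only to about 36 h on Day 1, and no limit on AUCextr is set.
- AUCextr is listed per subject, and in the mono-exponential case it shows the missed fraction directly. It is not tied to the reading of the AUC0-t ratio.
- The Sequence 2 ratio carries the same artefact. With equal tlast, dividing the Sequence 1 ratio by it gives 1.000 under no interaction. This is a useful control, but no between-sequence PK contrast is prespecified, and Protocol 8.4.3.2 omits Sequence 2.
- SAP 8.4 allows further PK parameters, so AUC0-36h could be derived. That is permission, not prespecification. SAP 5.1 labels analyses added after database lock or unblinding as post hoc. With no decision rule attached, that label costs little, but it is easily avoided.
- Matching at 24 h would have a tighter window (±10 minutes) and avoid the Day 2 dose. It recovers less of a real effect, though: at h = 10 h and clearance down 30% it gives 1.212, against 1.286 for 36 h and a true 1.429.

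These points hold the importance down. They do not supply a matched ratio or a rule for reading the unequal one.

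**Conclusion.** The concern holds. Followed as written, the plan gives an AUC0-t ratio expected to be above 1 with no interaction for any analyte whose 48 h or 72 h value counts on Day 15. The gap is confined to AUC0-t, since Cmax is unaffected. The size cannot be fixed from the documents: it ranges from nil, if nothing is quantifiable after 36 h, to 1.287 at an assumed 20 h half-life with mono-exponential decline to 72 h. All sizes rest on assumed half-lives and terminal shares. Importance is modest: the ratios are secondary, carry no bounds or decision rule, and are reported beside measures that partly expose the artefact. It is still worth correcting before database lock, because text alone does it.

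**What to change.** In Protocol 8.4.3.2 and SAP 8.5.2:

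1. Keep the AUC0-t and AUC0-inf ratios and add, without substituting, a Day 15/Day 1 AUC0-36h ratio with 90% CI for morphine, M6G and M3G in both sequences.
2. Define it to exactly 36 h. If the nominal 36 h sample is late, interpolate by the linear-up/log-down rule. If it is early or NQ and no later value is usable, extrapolate from tlast with lambda-z. If lambda-z is not reportable, exclude and list the subject.
3. Name AUC0-inf as the measure of total exposure.
4. State that the AUC0-t ratio covers unequal intervals and is not to be read alone as evidence of interaction when Day 15 tlast is beyond 36 h. Show it beside AUCextr for both days and the Sequence 2 ratio.
5. Footnote that the Day 1 36 h sample follows the first oral dose, since Protocol 5.3 says "On Days 2 to 15, an oral dose of the assigned treatment (either AZD4041 or Placebo) once daily will be administered to subjects".

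The cost is wording and one partial-AUC parameter. All samples to 36 h are already scheduled on both days, and no planned ratio is lost. The downside is one more ratio per analyte and sequence, and a measure that understates a real effect on late elimination, as the clearance-down-30% table shows. It must therefore be read with AUC0-inf.

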8 PHARMACOKINETIC ANALYSIS

The pharmacokinetic (PK) parameters from the concentration data for AZD4041, morphine, morphine-6-glucuronide and morphine-3-glucuronide will be derived using non-compartmental methods in Phoenix® WinNonlin® Version 8.3 or higher (Certara) by the Clinical PK Scientist from AstraZeneca.

8.1 Handling of Measurements Below the Lower Limit of Quantification in the PK analysis

For each PK sampling period, plasma concentrations that are non-quantifiable (NQ) from the time of pre-dose sampling ($t=0$) up to the time of the first quantifiable concentration is set to a value of zero. After this time point, NQ plasma concentrations are set to missing for all

concentration profiles. Where 2 or more consecutive concentrations are NQ at the end of a profile, the profile is deemed to have terminated and therefore any further quantifiable concentrations are set to missing for the calculation of the PK parameters unless it is considered to be a true characteristic of the profile of the drug.

If an entire concentration-time profile is NQ, the profile is excluded from the PK analysis.

Cmax, tmax, and tlast are taken directly from the concentration-time profiles.

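### No morphine sample at the end of the 10-minute infusion: parent Cmax and tmax are set by the schedule, AUC is biased low, and CL and Vz are biased high

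*Protocol*

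**What the plan says.** Protocol Section 5.3 gives the Day 1 dosing as follows: "a single intravenous infusion of morphine will be administered to the subjects over a 10-minute interval" (±30 seconds). Day 15 uses the same infusion, with the oral dose given within 1 minute of its end.

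Table 6-14 lists the Day 1 draws as "Day 1: predose, 5, 15, 30 minutes and 1, 1.5, 2, 3, 4, 6, 8, 12, 24, and 36 hours postdose" and the Day 15 draws as "Day 15: predose, 5, 15, 30 minutes and 1, 1.5, 2, 3, 4, 6, 8, 12, 24, 36, 48, and 72 hours postdose". Footnote a ties predose to the start of the infusion but adds: "Nominal times listed are relative to the end of morphine intravenous infusion". Table 6-16 allows ±1 minute for draws up to 30 minutes. Nothing is drawn during the infusion or when it stops.

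On derivation, SAP Section 8.1 says: "Cmax, tmax, and tlast are taken directly from the concentration-time profiles". It sets non-quantifiable values before the first quantifiable one to zero, with predose at t=0. SAP Table 8-2 uses linear up/log down for AUC, Dose/AUC0-inf for CL and CL/λz for Vz, the last two for the parent only. SAP Section 8.3 uses actual elapsed times from recorded sampling and dosing times, but does not say whether the morphine clock starts at the start or the end of the infusion.

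The results serve two separate secondary objectives: describing morphine PK, and the Day 15/Day 1 ratios of Cmax, AUC0-t and AUC0-inf with 90% confidence intervals (Protocol Section 8.4.3.2; SAP Section 8.5.2).

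**The concern.** During a constant-rate intravenous infusion under linear kinetics, parent drug rises until the infusion stops and then falls. The peak is at the one moment Table 6-14 does not sample. The value reported as parent Cmax is taken 4 to 6 minutes later, while drug may still be distributing quickly, and tmax lands on the first draw in essentially every subject.

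AUC is affected because the linear-up rule draws a straight line from zero at predose to the 5-minute value and cuts off the area around the peak. CL is dose divided by that AUC, so it is too high, and Vz follows CL.

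At stake are the absolute morphine figures (Cmax, tmax, AUC, CL, Vz), which answer their own secondary objective, and the meaning of the Cmax ratio as a comparison of peak exposure.

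**Working it through.** The plan states no figure on this point, so there is none to reproduce.

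**Inputs from the documents.** Infusion length T = 10 min; draws at 5, 15 and 30 min and so on after the end of infusion; ±1 min window; predose = 0; linear up/log down; AUC0-inf = AUC0-t + Clast/λz; CL = Dose/AUC0-inf; Vz = CL/λz.

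**Assumption (not in the documents).** Bolus response A·exp(-αt) + B·exp(-βt), with distribution half-life 2-10 min, terminal half-life 120 min and A/B = 5 or 10. Draws are used to 12 h.

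**Formulae.**
- End of infusion: C(T) = Σ Ai/(αi·T) × (1 - exp(-αi·T)).
- Later, at s minutes after the end: each term is multiplied by exp(-αi·s).
- True AUC0-inf = Σ Ai/αi.

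**One case in full** (half-lives 5 and 120 min, A = 5, B = 1; α = 0.1386, β = 0.005776 per min):
- C(T) = 5/1.386 × 0.75 + 1/0.05776 × 0.0561 = 2.705 + 0.972 = 3.677.
- C at 5 min = 2.705 × 0.5 + 0.972 × 0.9715 = 2.297. Ratio 2.297/3.677 = 0.62.
- True AUC = 5/0.1386 + 1/0.005776 = 36.1 + 173.1 = 209.2.
- Area over the first 15 min: the straight line gives 15 × 2.297/2 = 17.2, against a true 36.0. The shortfall is 18.8, or 9.0% of the total. The log-down rule on a convex curve gives a little back later, so AUC0-inf is 91.7% of true.
- CL: 1/0.917 = 1.09, so 9% too high. Vz is too high by the same factor, since λz is unaffected.

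**Across the assumed range** (time zero = start of infusion; values are % of true):

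| Distribution half-life, A/B | 5-min value / peak | AUC0-inf as planned | AUC0-inf, end-of-infusion draw | AUC0-inf, back-extrapolated |
|---|---|---|---|---|
| 2 min, 5 | 50 | 92.6 | 98.7 | 94.9 |
| 2 min, 10 | 38 | 87.5 | 97.4 | 90.6 |
| 3 min, 5 | 53 | 91.8 | 98.8 | 95.4 |
| 3 min, 10 | 45 | 86.3 | 97.7 | 92.2 |
| 5 min, 5 | 62 | 91.7 | 99.3 | 97.4 |
| 5 min, 10 | 57 | 86.7 | 98.6 | 96.2 |
| 10 min, 5 | 76 | 93.2 | 100.0 | 99.6 |
| 10 min, 10 | 74 | 90.1 | 99.8 | 99.4 |

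CL is therefore between 1/0.932 - 1 = 7% and 1/0.863 - 1 = 16% too high. Back-extrapolating the 5- and 15-minute values recovers only 48-98% of the peak itself, and is worst where distribution is fastest.

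**Outside that range.** A wider set with two or three exponentials (fastest half-life 1.5-15 min) gave a 5-minute value of 35-88% of the peak and AUC 3-20% low. With one compartment and a half-life of 90-180 min, the 5-minute value is 0.5^(5/90) = 96% to 0.5^(5/180) = 98% of the peak and AUC is 1-2% low. The direction was the same in every case.

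**Effect on the ratio.** With no interaction the bias cancels. If clearance fell by 20% (true AUC ratio 1/0.8 = 1.25), the observed AUC ratio would be 1.27-1.32 across three assumed profiles and either choice of time zero. The observed Cmax ratio would be 1.05-1.12 against a true 1.02-1.05.

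**The case against.** The strongest reply is that the only planned inference on morphine PK is the within-subject Day 15/Day 1 ratio. The early draws are identical on both days, and Sequence 2 supplies a parallel ratio under placebo on the same schedule. That stands. A reader might infer that the interaction analysis is invalid, but the documents do not support this: the bias cancels under no interaction and only mildly overstates a real one.

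A reader might also infer that the ±1 minute window makes the Cmax ratio unusable, since the 4- and 6-minute values differ by 11-28% of the 6-minute value. Those are opposite edges of the window. With draws spread evenly over it, timing adds an SD of 0.04-0.11 to the log ratio. For 24 completers and an assumed 30% SD of the log ratio, the 90% CI half-width goes from 1.714 × 0.30/√24 = 0.105 to at most 1.714 × √(0.30² + 0.11²)/√24 = 0.112. The added noise is modest. Recorded actual times also carry timing deviations into AUC, although they do not correct Cmax.

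Cmax is defined as the maximum observed concentration, so the plan will report what it defines. That is fair, but a reader will take an infusion Cmax as the peak, and the definition does nothing for AUC, CL or Vz.

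A larger loss (AUC 79-89% of true under the same profile) follows if time zero is the end of infusion, because the 10 infusion minutes then drop out. The documents do not say that. Predose is referenced to the start, and the SAP is silent on the clock for AUC, so this is only a possible reading.

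Finally, the size rests on disposition values that the documents do not give. That also stands, and is why ranges are shown.

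**Conclusion.** The point holds for parent morphine. Followed as written, the plan gives a Cmax about 5 minutes past the peak, a tmax dictated by the schedule, AUC too low, and CL and Vz too high. The mechanism needs only linear kinetics and a constant-rate infusion.

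The amount is conditional. Under the assumed two-compartment range the first value is 38-76% of the peak, AUC is 86-93% of true and CL is 7-16% high, with time zero at the start of infusion. In a one-compartment limit AUC is 1-2% low. No single bias figure can be claimed from the documents.

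A reader might extend this to everything in Table 6-14 or to the trial's main conclusion. Neither follows. Morphine-6-glucuronide and morphine-3-glucuronide form after dosing, so a missed end-of-infusion draw should matter much less for them, and CL and Vz are planned for the parent only. The primary respiratory endpoints do not use these data. The matter is worth correcting because describing morphine PK is a secondary objective in its own right, which the ratio does not rescue.

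**What to change.** **Preferred.** Add an end-of-infusion sample for morphine on Days 1 and 15. State in SAP Sections 8.3 and 8.4 that time zero for the morphine non-compartmental analysis is the start of infusion, with the actual infusion duration. Under the same assumptions AUC becomes 97-100% of true and Cmax is the measured peak. The cost is a protocol change and one small draw on each of two already densely sampled days. Draws are by direct venipuncture unless a cannula is used, and on Day 15 the draw must be coordinated with the oral administration due within 1 minute of the end of infusion.

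**If no draw is added** (for example, because sampling is complete), amend the SAP to:
- use start-of-infusion time zero;
- impute the end-of-infusion concentration by log-linear back-extrapolation of the 5- and 15-minute values, for AUC only;
- report the first observed value as C5min, not as peak Cmax;
- rest the parent interaction conclusion on AUC;
- flag CL and Vz as approximate.

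This costs SAP wording only, but it is a partial correction: AUC reaches about 91-100% of true under the same assumptions, and the peak itself is not reliably recovered.
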